## 5.6.3 Clinical Laboratory Evaluation

### 5.6.3.1 Hematology and Biochemistry

Hematology and biochemistry safety parameters are measured at Visit 1 (screening), Visit 2 (Day 1), Visit 3, Visit 4, Visit 6, Visit 8 (end of treatment) and Visit 9 (end of taper).

Summaries will be presented by treatment group for each laboratory parameter at each visit. Change from baseline to each post-baseline visit will also be presented.

If values for any of the parameters are below or above the limit of quantification of the assay (BLQ or ALQ), then they will be included in the summary tables at the BLQ or ALQ thresholds. However, for estimated creatinine clearance, results >60 are reported only as '>60'. Hence, estimated glomerular filtration rate (eGFR) will be calculated as:

For patients who are ≥18 years at screening, the Cockcroft-Gault equation will be used:

$$\text{eGFR (mL/min)} = [(140 - \text{age}) \times \text{weight} \times k] / \text{serum creatinine}$$

where age is measured in years, weight is measured in kg,  $k = 1.23$  if male,  $k = 1.04$  if female and serum creatinine is measured in  $\mu\text{mol/L}$ . eGFR will be indexed to body surface area (BSA) using the following formula:

$$\text{eGFR (mL/min/1.73m}^2\text{)} = \text{eGFR (mL/min)} \times 1.73/\text{BSA}$$

where BSA is based on the Du Bois and Du Bois formula:

$$\text{weight}^{0.425} \times \text{height}^{0.725} \times 0.007184$$

where weight is measured in kg and height is measured in cm.

For patients who are <18 years at screening, the revised Schwartz estimate will be used:

$$(36.2 \times \text{height}) / \text{serum creatinine}$$

where height is measured in cm and serum creatinine is measured in  $\mu\text{mol/L}$ . When available, enzymatic serum creatinine will be used. Otherwise, the Jaffe serum creatinine will be used. If height or weight is missing at the collection date, then the closest value to the sample date will be used. If there is more than one height or weight value on the same day or 2 height or weight values equally distant from the collection date, then the mean will be used. The eGFR will be summarized separately for each method.

Where laboratory samples are repeated, the baseline value is defined as the final recorded value prior to the first dose of IMP. If the Visit 2 data are missing then, where possible, the Visit 1 measurements will be used as baseline.

Shift tables for hematology and biochemistry parameters will be constructed, based upon normal ranges and GW toxicity limits (See Section 8), to determine the categorical shifts from baseline to each post-baseline visit. Values will be categorized as 'Normal', 'Low' or 'High' based on normal ranges and 'Toxically Low', 'Toxically Normal' or 'Toxically High' based on GW toxicity limits.

For eGFR, results will be assigned to the following grades:

- Normal: >60 ml/min/1.73 m^2
- Grade 1: 60 ml/min/1.73 m^2
- Grade 2: ≥30 and <60 ml/min/1.73 m^2
- Grade 3: ≥15 and <30 ml/min/1.73 m^2

- Grade 4: <15 ml/min/1.73 m^2

A separate shift table will be produced for eGFR based upon the above grades to determine the categorical shifts from baseline to each post-baseline visit.

Scatter plots will be produced for each laboratory parameter presenting the maximum post baseline result divided by the upper limit of normal (ULN) on the Y-axis, and the baseline result divided by the ULN on the X-axis. However, for prothrombin international normalized ratio (INR), both axes will present the raw results rather than dividing by ULN.

An additional table will be produced, summarizing the number of patients meeting the following criteria:

- Alanine aminotransferase (ALT) > 1×ULN at baseline
- Aspartate aminotransferase (AST) > 1×ULN at baseline
- AT > 1×ULN at baseline
- Treatment emergent ALT > 3×ULN, > 5×ULN and > 8×ULN
- Treatment emergent AST > 3×ULN, > 5×ULN and > 8×ULN
- Treatment emergent AT > 3×ULN, > 5×ULN and > 8×ULN
- Treatment emergent AT > 3×ULN and either bilirubin > 2×ULN or INR > 1.5

where AT is AST or ALT, and treatment emergent is defined as criteria not met at baseline, but met at any time post-baseline. The above will be summarized overall and for the following subgroups: Sex (Male, Female).

- Valproic acid use (Yes, No).
- Clobazam use (Yes, No).
- Valproic acid use and Clobazam use (Yes/Yes, Yes/No, No/Yes, No/No).
- Patients taking 3 or more current AEDs.
- Patients taking 4 or more current AEDs.

A separate table will be produced, by treatment group and visit, presenting the incidence of patients with urinalysis or blood results indicative of a medical condition at Visit 1 and indicative of an AE after Visit 1.

All laboratory data will be listed; listings will include limited demographic information about the patient (age, sex, race and weight at baseline). Abnormal laboratory values will be listed separately. A further listing will be created for the laboratory reference ranges and toxicity limits.

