Table 12.10	Summary of Treatment-Related Treatment Emergent Adverse Events Leading to Permanent IMP Dose Reduction Excluding Permanent Discontinuation and by Resolution and Overall	Safety Analysis Set
Table 12.11	Summary of Fatal Treatment Emergent Adverse Events	Safety Analysis Set
Table 12.12	Summary of Serious Treatment Emergent Adverse Events by Event	Safety Analysis Set
Table 12.13	Summary of Treatment-Related Serious Treatment Emergent Adverse Events by Event	Safety Analysis Set
Table 13.1.1	Summary of Laboratory Safety Parameters – Hematology	Safety Analysis Set
Table 13.1.2	Summary of Laboratory Safety Parameters – Biochemistry	Safety Analysis Set
Table 13.2.1	Shift Table for Hematology Laboratory Parameters – Based on Reference Ranges	Safety Analysis Set
Table 13.2.2	Shift Table for Biochemistry Laboratory Parameters – Based on Reference Ranges	Safety Analysis Set
Table 13.3.1	Shift Table for Hematology Laboratory Parameters – Based on Toxicity Limits	Safety Analysis Set
Table 13.3.2	Shift Table for Biochemistry Laboratory Parameters – Based on Toxicity Limits	Safety Analysis Set
Table 13.3.3	Shift Table for eGFR – Based on Derived Grades	Safety Analysis Set
Table 13.4	Summary of Liver Parameter Flags	Safety Analysis Set
Table 13.5	Incidence of Laboratory Abnormalities	Safety Analysis Set
Table 13.6	Summary of Pregnancy Test and Urine THC Screen Results	Safety Analysis Set
Table 14.1.1	Summary of Vital Signs	Safety Analysis Set
Table 14.1.2	Incidence of Clinically Significant Changes from Baseline for Vital Signs	Safety Analysis Set
Table 14.1.3	Incidence of Defined Flagged Vital Signs	Safety Analysis Set

Table Number	Title	Analysis Set
Table 14.1.4	Incidence of Vital Signs Abnormalities	Safety Analysis Set
Table 14.2.1	Summary of ECG Parameters	Safety Analysis Set
Table 14.2.2	Incidence of Defined Flagged ECG Parameter Values	Safety Analysis Set
Table 14.2.3	Incidence of ECG Abnormalities	Safety Analysis Set
Table 14.3.1	Summary of Children's Columbia-Suicide Severity Rating Scale	Safety Analysis Set
Table 14.3.2	Summary of Children's Columbia-Suicide Severity Rating Scale by Type	Safety Analysis Set
Table 14.4	Incidence of Physical Examination Abnormalities	Safety Analysis Set
Table 14.5	Summary of Tanner Stages	Safety Analysis Set
Table 14.6	Summary of Menstruation Details	Safety Analysis Set
Table 14.7	Summary of Cannabis Withdrawal Scale (18 Years)	Safety Analysis Set

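### The SAP's eGFR grading leaves Grade 1 only the exact value 60, and its shift table cannot show any fall in eGFR that stays above 60

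*SAP*

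**What the plan says.** SAP section 5.6.3.1 explains that for estimated creatinine clearance "results >60 are reported only as" exceeding 60. It therefore has eGFR recalculated, by the revised Schwartz formula below 18 years and by Cockcroft-Gault indexed to body surface area from 18 years.

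The recalculated values are then graded:

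- "Normal: >60 ml/min/1.73 m"
- "Grade 1: 60 ml/min/1.73 m"
- "Grade 2: ≥30 and <60 ml/min/1.73 m"
- Grade 3 covers 15 to just under 30, and Grade 4 anything below 15.

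Of their use the SAP says: "A separate shift table will be produced for eGFR based upon the above grades". SAP Table 13 lists this output as Table 13.3.3, "Shift Table for eGFR – Based on Derived Grades". No rounding rule for grading is given.

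The same section plans by-visit summaries of each laboratory parameter with change from baseline, and shift tables against the normal range and against toxicity limits. SAP Table 11 sets the creatinine toxicity limit at 2.6 times the upper limit of the reference range (UL) or more.

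**The concern.** Two features of the grading do not serve a shift table. First, Normal and Grade 2 meet at 60 from either side, so one of the five classes is a single point on a continuous derived scale. Second, eGFR is recalculated because the laboratory value is censored above 60, yet within this table the grading puts every value above 60 back into one class.

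At stake is how the table is read. Table 13.3.3 is the only listed output that classifies eGFR by grade. A row of Normal-to-Normal patients could be taken to mean that nobody had a material fall, at either dose level, when the table can only say that nobody reached 60 or below.

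**Working it through.** **Inputs.** The grade limits and eGFR formulas are from SAP 5.6.3.1, and the creatinine toxicity limit is from SAP Table 11. The heights, weight and creatinine values in step 3 are assumptions for illustration. The documents give no baseline distribution of eGFR or creatinine and no numerical reference limits for creatinine. The plan states no figure of its own to reproduce.

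**Step 1: width of Grade 1.** Applying the limits as written, 60.01 is Normal, 60 is Grade 1 and 59.99 is Grade 2. A symbol lost in text extraction would not change this, because any wider Grade 1 would overlap Normal or Grade 2, and both of those are legible.

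On a grid of heights 80.0 to 185.0 cm in 0.1 cm steps and whole-number creatinine 15 to 120 µmol/L, none of the 1,051 × 106 = 111,406 Schwartz values equals 60. If eGFR were first rounded to an integer, about 1.3% would. The grid is unweighted and is not a patient distribution.

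**Step 2: the largest fall that stays Normal.** With baseline eGFR B, the patient stays Normal while the fall is less than 1 − 60/B. With height unchanged under Schwartz, this means creatinine rises by a factor of less than B/60.

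| Baseline eGFR | Creatinine factor that reaches 60 | Fall staying Normal is below |
|---|---|---|
| 90 | 90/60 = 1.50 | 1 − 60/90 = 33.3% |
| 100 | 100/60 = 1.67 | 1 − 60/100 = 40% |
| 120 | 120/60 = 2.00 | 1 − 60/120 = 50% |
| 150 | 150/60 = 2.50 | 1 − 60/150 = 60% |

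Halving eGFR leaves the patient Normal only if B/2 > 60, that is B > 120. From exactly 120 it gives Grade 1, and from above 60 but below 120 it gives Grade 2.

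**Step 3: examples with creatinine doubled (assumed inputs).**

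- 110 cm, 30 to 60 µmol/L: 36.2 × 110/30 = 132.7, and 36.2 × 110/60 = 66.4. Normal to Normal.
- 130 cm, 40 to 80 µmol/L: 36.2 × 130/40 = 117.7, and 36.2 × 130/80 = 58.8. Normal to Grade 2, so the shift is visible.
- Age 18, male, 55 kg, 165 cm, 60 to 120 µmol/L, by indexed Cockcroft-Gault: 148.9 to 74.4. Normal to Normal.

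**Step 4: does the creatinine grading cover the gap?** If baseline creatinine is at or below UL, a doubling reaches at most 2.0 × UL, which is under the 2.6 × UL toxicity limit. If baseline is at or below half of UL, the doubled value is at most 1.0 × UL, so the normal-range shift does not register it either. From a baseline above half of UL and up to UL, the normal-range shift does register it.

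**The case against.** The strongest reply is that this is one descriptive table among several renal outputs.

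- SAP 5.1 requires minimum and maximum for continuous variables, and SAP 5.6.3.1 applies summaries and change from baseline to each laboratory parameter, with eGFR summarized separately by method. The first child in step 3 would contribute a change of 132.7 − 66.4 = 66.3, and the minimum at each visit would show the largest fall.
- The creatinine shift on normal ranges does count patients who move from normal to high.
- The scatter plots use the maximum post-baseline value. That is the wrong direction for eGFR, but it would display a rise in creatinine.
- Results judged to indicate an adverse event are tabulated by group and visit (Table 13.5). All laboratory data are listed, with abnormal values listed separately. Protocol 9.1.9 has an investigator review every result.
- The documents contain no renal endpoint or renal withdrawal rule, and a near-empty Grade 1 row misclassifies nobody.

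All of this stands, and it limits the point. What it does not supply is a count of patients by size of fall in eGFR: the summaries describe groups and extremes, the creatinine shift depends on where UL lies, and the listings are not tabulated.

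A reader might also infer that the table can show no mild or moderate decline at all. The documents do not support that. Every fall to 60 or below appears, which from a baseline of 100 means any fall of 40% or more. Nor is the recalculated information above 60 lost to the analysis, since it feeds the continuous summaries.

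**Conclusion.** The point holds for Table 13.3.3. Grade 1 is a single value as written, and any fall that stays above 60 is invisible in that table. The possible size of a hidden fall grows with baseline eGFR, as step 2 shows.

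A reader might go further and say that a child can lose half of kidney function unnoticed. That requires a baseline eGFR above 120 and refers to this table alone. How many patients start above 120 cannot be determined from the documents.

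The limits on hidden falls follow directly from the SAP's cuts and need no outside figure. The near-emptiness of Grade 1 assumes grading on unrounded or finely rounded values, which the SAP leaves open. The matter is minor: it concerns descriptive safety reporting and does not touch the primary analysis.

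**What to change.** In SAP 5.6.3.1, keep the cut at 60 and make three changes.

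1. Give Grade 1 a real interval or remove it. An interval would start at 60 and need an upper bound, chosen and justified by the sponsor because the documents supply none; Normal would then start at that bound. If Grade 1 is removed, say which class takes the value 60.
2. State whether eGFR is rounded before grading, and to what precision.
3. Add to Table 13.3.3, by treatment group, the number and percentage of patients whose eGFR falls from their own baseline by at least a prespecified percentage at any post-baseline visit. Falls of 25% or more and 50% or more would serve, marked as chosen descriptive cuts. SAP 5.6.3.1 already counts patients against several thresholds for ALT and AST, so the format exists.

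The cost is a few lines of SAP text and one more table block, using values already derived. The downside is that more patients will be shown with mild falls, some of which may be ordinary variation in creatinine. The placebo columns give the comparison for that.

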### 5.6.3.2 Urinalysis

Urinalysis is assessed, using dipsticks, at the same visits as biochemistry and hematology.

Urinalysis results will be listed only.

### 5.6.3.3 Pregnancy Test and Urine THC Screen

Serum pregnancy test results and urine THC screen results will be summarized by treatment group and visit.

---

## 5.6.4 Vital Signs, Other Physical Findings and Other Safety Data

### 5.6.4.1 Vital Signs

Vital signs (systolic blood pressure, diastolic blood pressure, pulse rate, temperature and respiratory rate) are measured at Visit 1 (screening), Visit 2 (Day 1), Visit 3, Visit 4, Visit 6, Visit 8 (end of treatment) and Visit 9 (end of taper).

At Visit 1 and Visit 2, systolic and diastolic blood pressure are collected in the sitting, supine and standing positions. At all other visits, systolic and diastolic blood pressure are collected in the sitting position only.

Summaries will be presented by treatment group for each vital sign parameter at each visit. Change from baseline to each post-baseline visit will also be presented.

A separate table will be produced, by treatment group and visit, presenting the incidence of patients with vital signs indicative of a medical condition at Visit 1 and indicative of an AE after Visit 1.

Based on the criteria presented in Section 8, potentially clinically significant changes from baseline in vital signs measurements and other defined flagged values will be identified at each visit. The number of patients with a potentially clinically significant change from baseline will be summarized by parameter, visit and treatment group. The number of patients with at least one post-baseline flagged vital sign parameter value will be summarized by parameter, flagged criteria and treatment group.

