### 6.1 Inclusion Criteria

For inclusion in the study, patients must fulfil ALL of the following criteria:

- 6.1.1 Patient and/or parent(s)/legal representative must be willing and able to give informed assent/consent for participation in the study (see [Section 15.2](#)).
- 6.1.2 Patient and their caregiver must be willing and able (in the investigator's opinion) to comply with all study requirements.
- 6.1.3 Patient must be male or female aged between two and 18 years (inclusive).
- 6.1.4 Patient must have a documented history of DS which is not completely controlled by current AEDs.
- 6.1.5 Patient must be experiencing **four or more** convulsive seizures (i.e., tonic-clonic, tonic, clonic, atonic seizures) during the first 28 days of the baseline period.
- 6.1.6 Patient must be taking one or more AEDs at a dose which has/have been stable for at least four weeks.
- 6.1.7 All medications or interventions for epilepsy (including ketogenic diet and VNS) must have been stable for four weeks prior to screening and patient and caregiver are willing to maintain a stable regimen throughout the study. The ketogenic diet and VNS treatments are not counted as an AED.
- 6.1.8 Patient and/or parent(s)/legal representative is willing to allow his or her primary care practitioner and consultant to be notified of participation in the study.

- 6.1.9 Patient has completed their IVRS telephone diary on at least 25 days of the baseline period; patients who are non-compliant will be deemed ineligible to continue.

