### **9.2.8 Visit 8 (Day 99, End of Treatment/Withdrawal Visit)**

This visit will occur 98 days after randomization (Visit 2) or earlier if the patient withdraws from the study. A visit window of  $\pm 3$  days from the scheduled visit date is permitted, but it is preferred that the visit is performed on the scheduled visit day where possible. Patients will be instructed to record the dosing time of their concomitant AEDs in the diary. They will also be asked to record their meal times the day before and the day of Visit 8.

The following assessments will be made at Visit 8 / the Withdrawal visit: vital signs, physical examination (including height and body weight), ECG, EDSS, Sleep Disruption 0–10 NRS, CGIC, CGICSD, QOLCE, C-SSRS (Children's Since Last Visit), cognitive assessment battery (at participating sites), details of menstruation (for females), Tanner Staging (for patients aged 10–17 [inclusive], or earlier if clinically indicated by onset of menarche or other signs of precocious puberty) and the Vineland-II. The Caregiver Impression of IMP Palatability will also be assessed. Clinical laboratory samples (blood and urine [where possible]) will be taken for hematology, biochemistry, urinalysis, a urine THC screen (required), determination of serum IGF-1 levels and a pregnancy test (using a serum sample, as appropriate). The patient's IVRS report and paper diary will

be reviewed and the information recorded along with information regarding AEs, epilepsy-related hospitalizations, concomitant medications and/or changes to medication (including AEDs). The investigator must assess adherence to the dosing regimen.

Prior to the final dose of maintenance IMP, blood samples will be taken to determine plasma concentrations of CBD and its major metabolites (only patients who weigh  $\geq 20$  kg) and, provided the risk/benefit outcome is favorable in the investigator's opinion, concomitant AEDs (all patients). The final maintenance dose of IMP will then be taken in the clinic. ECG and vital signs will be re-assessed two to three hours post-dose. Further blood samples will be taken for CBD PK analyses. The presence of THC in plasma will also be assessed at a single time point (two to three hours post-dose). A urine sample will be collected (complete void) at the time of first blood sample collection for both CBD and THC analysis, and the exact urine volume will be recorded. See [Section 9.1.10](#).

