### 5.6.4.2 Electrocardiogram

An ECG will be performed at Visit 1 (screening), Visit 2 (Day 1), Visit 3, Visit 4, Visit 6, Visit 8 (end of treatment) and Visit 9 (end of taper).

Summaries will be presented by treatment group for ventricular rate, PR interval, QRS duration, QT interval and QTcB, at each visit. Change from baseline to each post-baseline visit will also be presented.

A separate table will be produced, by treatment group and visit, presenting the incidence of patients with an ECG indicative of a medical condition at Visit 1 and indicative of an AE after Visit 1.

Based on the criteria presented in Section 8, defined flagged values will be identified at each visit. The number of patients with at least one post-baseline flagged ECG parameter value will be summarized by parameter, flagged criteria and treatment group.

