**Table 10 Defined Flagged Values for ECG Parameters**

ECG Parameter	Flag
QTc	> 450, > 480, > 500

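### The vital-sign and ECG flag tables do not separate patients already outside a limit at baseline, and the QTc flags have no stated correction formula

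*SAP*

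**What the plan says.** For vital signs, SAP 5.6.4.1 states: "The number of patients with at least one post-baseline flagged vital sign parameter value will be summarized by parameter, flagged criteria and treatment group". For ECG, SAP 5.6.4.2 states: "The number of patients with at least one post-baseline flagged ECG parameter value will be summarized by parameter, flagged criteria and treatment group". In both, one flagged reading after baseline is enough, and baseline status plays no part.

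The limits are fixed. Table 9 flags pulse below 60 or above 100, respiratory rate below 12 or above 20, temperature below 36.0 or above 38.0, and set levels of sitting blood pressure. Table 10 flags QTc at "> 450, > 480, > 500". None varies with age, although Protocol 6.1 admits patients from two to 18 years.

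The liver table in SAP 5.6.3.1 works differently: "treatment emergent is defined as criteria not met at baseline, but met at any time post-baseline". Hematology and biochemistry also get shift tables from baseline.

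The ECG summaries cover "ventricular rate, PR interval, QRS duration, QT interval and QTcB". QTcB is the only corrected interval named in the SAP. Table 10 says only QTc.

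**The concern.** A count of patients with any flagged reading on treatment mixes two groups: those who crossed the limit after starting IMP, and those who were beyond it before the first dose. Only the first group bears on the drug. If a limit is one that many young children exceed at rest, the second group raises the percentage in every arm. The table then overstates on-treatment abnormality, and its contrast with placebo is blunted.

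Vital signs and ECG are named safety variables, assessed at each dose level against placebo (SAP 3.3.3). The SAP gives no reason for applying a baseline condition to liver tests and not here.

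The QTc flags raise a related point. Bazett's correction lengthens QTc as heart rate rises, so a fast pulse alone can push a reading over 450.

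**Working it through.** **1. Baseline reference across the SAP's categorical safety outputs**

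| Output | Baseline considered? |
|---|---|
| Liver criteria (5.6.3.1) | Yes, treatment-emergent rule |
| Hematology and biochemistry shifts (5.6.3.1) | Yes |
| Vital-sign change counts (Table 8): sitting systolic BP, sitting diastolic BP, pulse, weight | Yes, change from baseline |
| Vital-sign flags (Table 9): BP, pulse, temperature, respiratory rate | No |
| QTc flags (Table 10) | No |

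Respiratory rate, temperature and QTc appear only in the last two rows.

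**2. Readings that can trigger a flag.** Baseline is the last measure before the first dose (SAP 5.1.3.1). Visits 3, 4, 6 and 8 give 4 later readings, and Visit 9 gives a fifth for those who attend it. At Visit 8 "ECG and vital signs will be re-assessed two to three hours post-dose", and Protocol 9.2.2 requires the same at Visit 2. The maximum is therefore 5 + 2 = 7. The SAP does not say whether the post-dose readings count.

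**3. Effect on the table.** The SAP states no expected flag rate, so there is no figure to reproduce. The following is an illustration by simulation.

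- Model: each reading = patient level + visit noise, total variance 1, within-patient correlation ρ. A reading is flagged above c, where c is set so that a share q is flagged at baseline.
- Planned count: P(at least one of k readings > c). Treatment-emergent count: the same probability among patients whose baseline reading was not above c.
- From the documents: k = 4 or 7, and 62 patients per group (SAP 3.2).
- Assumed: q, ρ = 0.5 or 0.7, and a drug shift of 0.5 SD toward the limit.
- Patients unflagged at baseline per arm = 62 × (1 − q); for example 62 × 0.5 = 31.

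| q | Planned: placebo vs drug (gap, points) | Emergent: placebo vs drug (gap, points) | Unflagged per arm |
|---|---|---|---|
| 1% | 3-5% vs 9-15% (6-10) | 2-5% vs 8-14% (6-10) | 61 |
| 5% | 12-20% vs 26-41% (14-20) | 9-18% vs 23-38% (14-20) | 59 |
| 20% | 38-55% vs 59-77% (21-23) | 26-47% vs 50-72% (24-25) | 50 |
| 50% | 73-87% vs 88-96% (9-15) | 51-78% vs 76-93% (15-25) | 31 |
| 80% | 94-99% vs 98-100% (1-4) | 74-94% vs 91-99% (5-17) | 12 |

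The planned count approaches its ceiling only when about half or more of patients start outside the limit.

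**4. Would replacing the count help detection?** Power for a two-group comparison of the planned count, against the treatment-emergent count in the smaller denominator, is 42-54% against 38-53% at q = 50%, and 11-24% against 9-20% at q = 80%. There is a gain where readings persist strongly within a patient: at q = 20%, ρ = 0.85 and k = 4, power rises from about 62% to 72%. At ρ = 0.5 and the same q and k it falls slightly, from 72% to 69%.

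**5. What the planned change summaries would show.** For the same 0.5 SD shift at one visit, the SD of change is √(2(1 − ρ)), which is 1 at ρ = 0.5 and 0.775 at ρ = 0.7. With 62 per group, z = 0.5 / (SD × √(2/62)) − 1.96. This gives 0.82 and 1.63, or power of about 80% and 95% if the change were tested.

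**6. QT correction.** QTcB = QT/√RR and QTcF = QT/RR^(1/3), so QTcB/QTcF = RR^(−1/6), with RR in seconds.

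- 80 bpm: RR = 0.75, ratio 1.049 (5% higher).
- 120 bpm: RR = 0.5, ratio 1.122 (12% higher).
- Hypothetical reading, QT 320 ms at 120 bpm: QTcB = 320/0.707 = 453, flagged above 450. QTcF = 320/0.794 = 403, not flagged.

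**The case against.** The strongest reply is that these are two descriptive tables among several. The SAP plans change from baseline at every visit for each vital sign and for ventricular rate, PR, QRS, QT and QTcB. It counts potentially clinically significant changes for blood pressure, pulse and weight (Table 8). It tabulates findings indicative of an AE and lists individual values. Placebo columns sit beside the active arms. The liver thresholds also track the protocol's withdrawal and liver-injury criteria, so a stricter rule there may be deliberate. All of this stands, and it limits the point to what these two tables can show.

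Three stronger readings are tempting and are not supported.

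- A reader might infer that drug effects would be hidden from the report. The outputs above, and step 5 of the working, say otherwise.
- A reader might infer that the ECG counts will saturate as well. The lowest QTc cut-off is 450, and Protocol exclusion 6.2.4 removes clinically relevant ECG abnormalities at screening or randomization. Nothing in the documents suggests a large share flagged at baseline.
- A reader might multiply an assumed per-visit flag rate over independent visits and reach very high percentages. Independence contradicts the concern, which is about children who are persistently outside a limit. Under independence, baseline status predicts nothing and a treatment-emergent rule would leave the percentages unchanged.

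That Table 10 means Bazett is itself an inference from 5.6.4.2. Uncorrected QT and ventricular rate are shown beside QTcB, so a careful reader could spot a rate artifact. The flag count alone would not reveal it.

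**Conclusion.** The point holds as a gap in presentation. The flag tables do not distinguish new from pre-existing values, and for respiratory rate, temperature and QTc no other categorical output does. Mean changes by visit do not give the number of patients who newly crossed a limit.

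The size rests on the share outside each limit at baseline, which the documents do not give. At 5% or less the planned and treatment-emergent counts are close. From about 20% the planned percentages noticeably overstate new abnormality, and from about 50% the contrast with placebo is also blunted in that table. Such shares are most conceivable for pulse above 100 or respiratory rate above 20 in the youngest children. That is an assumption, and it would not extend to a limit such as systolic above 160.

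For ECG the point is narrower: baseline-flagged patients are not separated, and the correction behind the flags is unstated, with QTcB the only one planned. The 5% and 12% differences between corrections are exact arithmetic; how often they would change a flag in this trial is unknown. The primary analysis and type I error are unaffected. This is a worthwhile, inexpensive improvement.

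**What to change.** In SAP 5.6.4.1 and 5.6.4.2, keep the planned counts and add to both flag tables either:

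- a treatment-emergent column: criterion not met at baseline and met at any time afterwards, with patients unflagged at baseline as the denominator; or
- a shift from baseline to the worst post-baseline category.

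State the denominator explicitly, because the liver table defines treatment emergent without giving one. Adding is preferable to replacing: step 4 shows no general gain in power from the new count alone, and a replacement would drop patients who were flagged at baseline.

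State which QTc Table 10 refers to. Derive QTcF from the collected QT and ventricular rate, and apply the Table 10 flags to QTcF as well as QTcB.

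The cost is extra programming for two tables and one derived variable, with no new data. The drawback is a denominator that varies by parameter and can be small where many are flagged at baseline (about 31 per arm at a 50% share and 12 at 80%), so it should be printed beside each percentage.
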